7.2.3.1 Personalized Profiles

Participants will be asked to complete a brief online lifestyle risk assessment at the beginning and end of their participation in the program. Questions will be related to the content in the program courses (e.g. sleep, diet, and mindfulness/compassion). A personalized profile will be developed for each participant based on their responses to the lifestyle risk assessment. A visual

aide (e.g. sliding scale) will be used on the program dashboard to show the participant their risk level in each lifestyle domain.

7.2.3.2 Goal Setting

Participants will also be asked to set goals based on their risk profile and to re-visit and update their goals at the end of the 3 month program.

7.3 Facilitated discussion group

Participants will also participate in moderated remote discussion groups that will focus on learning and promotion of behavioral change. Discussion groups will occur approximately every 3 weeks and will be moderated by a social worker (ASW or LCSW) called HALT Helper Sessions will be filled on a rolling basis, with a variety of meeting times available to accommodate other commitments such as caregiving. Before each discussion group, the HALT Helper will review what the group is (and is not) and it will be made clear to participants that this is not group therapy but rather a facilitated discussion to focus on content that is being addressed in HALT-AD and to promote healthy lifestyle changes. Participants will also be reminded of the importance to maintain confidentiality during the group sessions and the limits to privacy/confidentiality due to the group setting at the beginning of each session.

7.4 HALT-AD Activity Data

The following data will be automatically collected through the HALT-AD program in order to evaluate user activity and engagement with the program:

Program Level Reporting	
Course Started %	How many users started the course
Course Complete %	How many users completed the course
Course Passed %	How many users passed the course
Minutes per learner	Average time spent per learner on a module
Average Score	Average Score per learner in a course
Participant Level Reporting	
Course Started %	How many courses were started by the learner
Course Complete %	How many courses were completed by the learner
Course Passed %	How many courses were passed by the learner
Minutes per Course	Average time spent per course

No identifiable information will be included in the study data set. All study data from HALT-AD will be de-identified and linked to the unique Participant ID prior to being included in the study database.

7.5 Compensation

Participants will be compensated \$100 in the form of a gift card for their time and effort. Compensation will be provided at the end of the study or upon early withdrawal. Early withdrawal after completion of Baseline will not impact the amount of compensation provided.

8.0 STUDY PROCEDURE DESCRIPTIONS

8.1 Sociodemographics

Sociodemographic data (sex, age, handedness, languages, marital/partner status, living circumstances, education, employment history) will be captured.

8.2 Medical/Surgical/Family History

Relevant medical and surgical history will be captured as well as relevant medical history of first-degree relatives. A list of current medications will also be documented.

8.3 Height/Weight/BMI

Participants will be asked to self-report current height and weight during the baseline visit. Responses will be used to calculate BMI using the NIH BMI Metric Calculator (https://www.nhlbi.nih.gov/health/educational/lose_wt/BMI/bmi-m.htm).

8.4 Hearing and Vision Assessment

Vision and hearing ability will be assessed by questions on perceived visual and auditory ability and an inventory of aids used. Participants must have relatively sufficient vision (with corrective lenses or other aids) so that they can identify symbols, stimuli and text presented on a computer screen in front of them. Participants must also have sufficient hearing (corrected with hearing aids or other voice amplification devices) to be able to follow spoken instructions and information that is presented only verbally.

9.0 STUDY-SPECIFIC INSTRUMENTS

9.1 Cognitive Measures

9.1.1 Montreal Cognitive Assessment-Telephone/Blind Version (T-MoCA)

The T-MoCA is a 5-10-minute test that has been validated for remote administration by telephone and provides a global assessment of cognition, covering domains of memory, language, attention and executive functioning [13]. The T-MoCA has been modified from the original MoCA to remove items requiring paper and pencil administration and visual stimuli. The total possible score is 22 with a cutoff score of greater or equal to 18 to indicate normal cognitive functioning.

9.2 Questionnaires

9.2.1 Knowledge Assessment Survey

Brief questionnaire that will be developed as the HALT-AD program content is finalized to assess general knowledge of dementia including risk factors, brain health and prevention. Participants' knowledge will be assessed pre and post participation in HALT-AD.

9.2.2 The New General Self-Efficacy Scale

Self-Efficacy is a concept that refers to one's global confidence in their ability to cope with demanding or novel situations. The New General Self-Efficacy scale is an 8-item 5-point likert scale (strongly disagree (1) to strongly agree (5)) which measure one's perceived competence in dealing with a range of stressful or challenging situations [14]. The scale will be completed online within HALT-AD.

9.2.3 Lifestyle Risk Assessment

Questionnaire to be developed by course leads to assess dementia risk based on HALT-AD Pilot Courses (e.g. Sleep, Diet, Physical Activity, Mindfulness/Compassion). Risk scores for each domain will be calculated.

9.2.4 HALT-AD User Experience Survey

Questionnaire adapted for HALT-AD based on questions from the User Experience Questionnaire (UEQ) available at <https://ueqtryitout.ueq-research.org/>. Participants will be asked to decide as spontaneously as possible which conflicting terms (e.g. annoying vs. enjoyable) better describes the HALT-AD program.

9.2.5 Net Promoter Score (NPS) Survey

The Net Promoter Score (NPS) Survey is a metric used in customer experience programs to measure the loyalty of customers to a product ([What is Net Promoter Score? \(Updated 2020\) | Qualtrics AU](#)). NPS scores are measured with a single question survey "How likely is it that you would recommend [Organisation X/Product Y/Service Z] to a friend or colleague?" and reported with a number from -100 to +100, a higher score is desirable.

9.2.6 HALT-AD Course Acceptability Survey

Questionnaire developed by the HALT-AD team to evaluate overall acceptability and satisfaction with the course content for the HALT-AD program. There are a total of 15 items including both multiple choice and open-ended questions (see Appendix 2).

9.2.7 HALT-AD Facilitated discussion group Acceptability Survey

Questionnaire to be developed in collaboration with the group facilitator. Questions will assess overall satisfaction and utility of the the monthly facilitated discussion groups.

10.0 EARLY DISCONTINUATION PROCEDURES

Participants are free to withdraw from study participation at any time, for any reason, and without prejudice.

Study Discontinuation for an individual participant may occur in the following circumstances:

1. Withdrawal of informed consent by the participant.
2. Adverse event or other significant medical condition which, in the opinion of the Investigator, render it necessary to remove the individual from study participation.
3. Any other occurrence that, in the Investigator's opinion, makes continued participation contrary to the participant's best interests.

If co-PIs discover sufficient reasonable cause for the premature termination of the study, the terminating party will provide written notification to the participant documenting the reason for study termination.

11.0 ADVERSE EVENTS

An adverse event (AE) is any untoward medical occurrence in a participant that occurs from the time of the baseline visit and up to 30 days after study participation has ended. For the purposes of reporting on the this study, an AE is defined as any unfavourable or unintended sign, symptom, or disease **associated with study participation** that is both non-serious and either temporally or causally related to study procedures. Pre-existing conditions, which increase in frequency or severity or worsen in nature during, or as a consequence of, a study procedure, may also be considered an AE if it meets the definition of being both non-serious and related to a study procedure. Adverse events that occur prior to the baseline visit will be documented as medical history.

An AE **does not** include:

- Medical or surgical procedures (e.g., surgery, endoscopy, tooth extraction, transfusion). The condition that leads to the procedure is the AE.
- Situations where an untoward medical occurrence has not occurred (e.g., hospitalization for elective surgery, social and/or convenience admissions).
- Worsening of symptoms associated with an associated co-morbid condition and not related to a study procedure.

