11.1 Evaluation and Reporting of Adverse Events

All AEs (i.e., a new event or an exacerbation of a pre-existing condition) that occur from the baseline visit to the end of the pilot study and are related to the study procedures will be recorded as an AE in the study database. Adverse events that occur prior to the baseline visit will be documented as medical history. The Investigator will follow all AEs until the AE

resolves, or until the Investigator determines the event is chronic or clinically stable. If an AE remains unresolved at the conclusion of the study, the Investigator will make a clinical assessment to determine whether continued follow-up of the AE is warranted.

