11.2 Assessment of Adverse Events

All AEs will be promptly documented on the Adverse Event CRF and assessed by the Investigator. Details of the event will include the dates of onset and resolution, severity, relationship to study procedures, seriousness, whether the event caused the participant to withdraw from the study, and outcome.

Severity: Severity will be graded and recorded according to the table below.

Severity	Definition
Mild	Awareness of event but easily tolerated
Moderate	Discomfort enough to cause interference with usual activity
Severe	Inability to carry out usual activity, incapacitating, requires medical intervention

Relationship: The relationship of the AE to study procedures will be determined by the Investigator, and assessed using the following definitions:

Relatedness	Description
Not Related	There is no evidence of a causal relationship and a causal relationship cannot be reasonably attributed to the study procedures. The event is clearly due to extraneous causes.
Unlikely Related	A poor temporal relationship exists between the event onset and study procedures. The event could easily be explained by the participant’s clinical state, intercurrent illness, or concomitant therapies.
Possibly Related	A relationship cannot be ruled out with certainty and the event may be related. There is some evidence to suggest a causal relationship but the influence of other factors may have contributed to the event, such as the participant’s clinical condition or concomitant treatment.
Probably Related	The event is likely related to study participation. There is evidence to suggest a causal relationship, such as reasonable temporal sequence from procedure. The influence of other factors is unlikely.
Definitely Related	The event is clearly related to study participation. There is clear evidence to suggest a causal relationship. The influence of other factors can be ruled out.

These criteria, in addition to good clinical judgment, should be used as a guide for determining the causal assessment.

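### Section 11 contradicts itself on whether serious adverse events are recorded, and gives two different end dates for recording (minor)

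*Combined protocol and SAP*

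**What the plan says.** Section 11.0 opens with a broad definition: any untoward medical event in a participant, "from the time of the baseline visit and up to 30 days after study participation has ended". The next sentence narrows this for reporting to an event "that is both non-serious and either temporally or causally related to study procedures". A pre-existing condition that worsens may count as an AE only "if it meets the definition of being both non-serious and related to a study procedure".

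Section 11.1 covers all AEs, which it explains as new events or exacerbations of existing conditions. It says that those "that occur from the baseline visit to the end of the pilot study and are related to the study procedures will be recorded" in the study database. It adds no condition on seriousness.

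Section 11.2 sends all AEs to the AE case report form. The details required include "relationship to study procedures, seriousness, whether the event caused the participant to withdraw from the study, and outcome". It then defines three grades of severity and five of relatedness. The two lowest relatedness grades are Not Related and Unlikely Related. Seriousness gets no definition there.

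**The concern.** Three sections meant to work as one rule do not agree on which events enter the database. The reporting definition removes serious events, while the form has a field that makes sense only if serious events are included. Staff who follow 11.0 to the letter would leave out the events that safety recording most needs to capture.

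The severity scale does not fill the gap. A Severe event is defined as "Inability to carry out usual activity, incapacitating, requires medical intervention". Under 11.0, whether such an event is recorded depends on whether it is also serious, a word that the protocol never explains.

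The last day on which an event counts also depends on which section is read. At stake is whether the safety record of the pilot is complete and is kept in the same way for every participant.

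**Working it through.** The plan gives no event count or rate for adverse events, so there is no figure of its own to reproduce. The check compares the passages and adds one line of arithmetic on the window.

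**1. Which events count**

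| Place | Seriousness | Relation to study procedures |
|---|---|---|
| 11.0, opening sentence | no limit | no limit |
| 11.0, reporting definition (stated twice) | non-serious only | related only |
| 11.1, recording rule | no limit of its own | related only |
| 11.2, details and grades | collected for each AE, not defined | includes Not Related and Unlikely Related |

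No two rows set the same rule. If the 11.0 reporting definition governs, every recorded AE is non-serious by definition, so the seriousness field can take only one value. If it does not govern, a serious related event is recorded, but the reporting sentences in 11.0 are then wrong.

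**2. Whether another section settles it**

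- The table of contents lists only 11.1 and 11.2 under section 11.
- The abbreviations list has AE but no term for a serious event.
- Section 13.4 deals with incidental findings, not with events.

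No section defines a serious event or says separately how one is recorded.

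**3. The end of the window**

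Both sections start at the baseline visit, so only the end differs. Let d be the number of days from the end of a participant's own participation to the end of the pilot.

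- 11.0 ends 30 days after participation ends.
- 11.1 ends d days after participation ends.
- A participant who finishes when the pilot ends has d = 0. The difference is 30 − 0 = 30 days, with 11.0 the longer.
- If the end of the pilot in 11.1 means each participant's own end, d = 0 for everyone and the 30 days apply to all.

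Now read 11.1 with the 11.0 definition. An event more than 30 days after participation ends is not an AE, so 11.1 cannot record it. The joint rule ends at the earlier of the two dates, min(30, d). Its shortfall against 11.0 is 30 − min(30, d). The synopsis (Study Duration) counts completion of data collection within the pilot period, so d is taken as not negative. The shortfall is then 30 days at d = 0, falls to 0 at d = 30, and stays at 0 beyond that. The range is 0 to 30 days.

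**The case against.** The strongest reply is that the narrow definition does not have to govern. The opening sentence of 11.0 has no seriousness limit, and 11.1 explains in its own words what it means by all AEs. Section 11.2 provides a seriousness field and a Severe grade. On the words of 11.1 and 11.2 alone, a serious related event goes on the form. This stands in part. A reader might infer that serious events have no recording route at all, and the documents do not support that. They support a conflict in which one stated rule drops these events and the others do not. The conflict is not harmless, because the 11.0 sentence says that it sets the definition for reporting, and it says so twice.

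A reader might also infer that the windows differ by months, with 11.1 running much longer for early withdrawals. That requires 11.1 to stand apart from the 11.0 definition. It would then also be free of the non-serious limit, and the first problem would weaken. The two claims cannot both be made at full strength. Nor is there support for 11.0 running more than 30 days longer. That would need participation to continue after the pilot ends, whereas the synopsis places completion of data collection inside it.

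The exclusion of "hospitalization for elective surgery, social and/or convenience admissions" might be taken as proof that serious events were meant to be included. It is weak evidence. It illustrates cases where nothing untoward happened, and the argument assumes that hospitalization counts as serious, which the protocol does not say.

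On relatedness, the two lowest grades could be the means by which the investigator decides that an event is not recorded, and the temporal alternative in 11.0 could admit an event with no causal link. Either is possible, but the protocol states neither, so the grades still need to be reconciled with the related-only limit.

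**Conclusion.** The contradiction is real and lies in current text. Section 11.0 limits reportable AEs to non-serious ones, 11.1 sets no such limit, and 11.2 collects an undefined seriousness. Under the 11.0 reporting definition a serious study-related event would not be recorded. The end dates differ by 30 days for a participant who finishes with the pilot. They differ by 0 to 30 days if 11.1 takes over the 11.0 definition and the pilot runs to completion of data collection. Both of those conditions are assumptions about how the text is meant.

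The point is minor. This is a pilot of 20 people, section 5.2.1 describes the risks as minimal, and no aim or listed outcome rests on AE data. The documents give no expected number of serious events. A reader might infer a gap in participant care. The documents do not support that: the conflict concerns what is written in the database, and 5.2.1 separately provides for breaks, skipped questions and an attempt at contact within 48 hours if negative emotions are mentioned.

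**What to change.** Four changes of wording, all in section 11:

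- Delete the non-serious condition in both sentences of 11.0. Both remain grammatical without it.
- Add a definition of seriousness to 11.2, beside those of severity and relatedness.
- State one end date for recording, in the same words, in 11.0 and 11.1.
- Reconcile the related-only limit in 11.0 and 11.1 with the Not Related and Unlikely Related grades in 11.2, so that it is clear whether such events are recorded.

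The AE form is not in the documents, so check that it carries the seriousness field that 11.2 calls for. The downside is possibly a few more events to log in 20 participants. No analysis, sample size or outcome changes.

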5.2 Potential Risks and Benefits Associated with this Study

5.2.1 Potential Risks

Risks associated with study participation are minimal and may include fatigue and/or frustration associated with cognitive screening at baseline and participating in an online educational program. Questionnaires on mood and lifestyle risk may increase negative affect. In order to mitigate these risks, participants will be reminded they can skip questions or take breaks. If a participant mentions negative emotions, the study coordinator will alert [name], co-PI and clinical psychologist, who will attempt to contact the participant within 48 hours to suggest mental health resources.

There may be limits in protecting confidentiality during facilitated group discussions and focus groups. Participants will be reminded to keep group discussions confidential but this cannot be guaranteed.

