7.1.3 Telephone Screening (within a month prior to baseline)

Following the pre-screening procedures described above, potentially eligible participants will be invited to complete the electronic informed consent process (see section 5.1). Once participants have electronically signed the ICF, the following procedures will be conducted remotely via telephone during the screening period (Estimated Time to Complete: up to 1 hour). Screening procedures may be completed over multiple days as long as all procedures are completed within 30 days prior to baseline. Procedures and instruments will be adapted for remote administration (see section 8.0 Study Procedure Descriptions and section 9.0 Study-Specific Instruments).

The following procedures will be conducted during the screening period (Estimated Time: 1.0-1.5 hours):

- Review of inclusion/exclusion criteria
- T-MoCA
- Hearing and Vision assessment
- Evaluation and confirmation of eligibility

Following completion of the screening assessments above, the co-PIs will be responsible for confirming participant eligibility to be enrolled in the study.

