7.1.4 Baseline/ HALT-AD Program Launch (+/- 30 days)

Participants who are confirmed to be eligible to participate and enrolled in the study, will then complete the following baseline assessments. These may be completed on the same day as the screening visit, as long as they are conducted following the screening assessments and confirmation of eligibility (total estimated time approximately 30 min):

- Documentation of demographics, medical history (including past medical procedures and family history), medications
- Self-Report Height, Weight
- Body Mass Index (BMI) calculation (based on self-report current height and weight)
- Knowledge Assessment Survey

Following completion of the above baseline assessments, participants will be enrolled in the HALT-AD online program and will be provided with instructions for logging into and beginning their participation in the program (see section 7.2 for a complete description of HALT-AD).

Participants will also complete the following baseline assessments directly within the online HALT-AD program (total estimated time approximately 30 min-1.0 hour):

- New General Self-Efficacy Scale (NGSE)
- Lifestyle Risk Assessment
- Goal setting

Throughout the participants' participation in the 3-Month HALT-AD program, a study coordinator will maintain contact with the participant by telephone or email to check-in with participants, provide reminders about upcoming HALT-AD program elements and be available to answer any questions that may arise. E-mails will be sent from a secure UCSD health e-mail account.

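### AE recording opens at baseline, but the T-MoCA, one source of the risks named in section 5.2.1, is given before baseline, so early reactions to it are filed as medical history

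*Combined protocol and SAP*

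**What the plan says.** **Start of the window.** Section 11.0 defines an AE as an event that "occurs from the time of the baseline visit and up to 30 days after study participation has ended". Section 11.1 has AEs entered in the study database if they are events "that occur from the baseline visit to the end of the pilot study and are related to the study procedures". Both sections send anything earlier to medical history; the wording in 11.0 is "Adverse events that occur prior to the baseline visit will be documented as medical history". Neither makes an exception for an event caused by a study procedure.

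**Named risks.** Section 5.2.1 calls the risks minimal and lists "fatigue and/or frustration associated with cognitive screening at baseline and participating in an online educational program". It adds that "Questionnaires on mood and lifestyle risk may increase negative affect" and that confidentiality in group sessions cannot be guaranteed. If a participant mentions negative emotions, the coordinator alerts a co-PI, who attempts contact within 48 hours.

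**When the test is given.** Section 7.1.3 reads: "Once participants have electronically signed the ICF, the following procedures will be conducted remotely via telephone during the screening period". The T-MoCA is on the list that follows. Appendix 1 marks the cognitive test in the Screening column only.

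**When medical history is taken.** Section 7.1.4 lists "Documentation of demographics, medical history (including past medical procedures and family history), medications" among the baseline assessments, which are completed by people already confirmed eligible and enrolled.

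**The concern.** The risk section and the AE section assume different timings for the same test. If the T-MoCA were given at baseline, as 5.2.1 says, the AE window would cover it. As actually scheduled, the test falls before the window opens, and a reaction to a post-consent study procedure is handled as if it were pre-existing history.

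What is at stake is how the safety record can be read. If the AE listing showed no events from cognitive testing, that could reflect the recording rule and not what participants experienced. The study is a pilot for a larger program, so the same wording could be carried forward.

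**Working it through.** No arithmetic applies. The check sets the stated timings side by side.

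| Step | Event | Source | AE window |
|---|---|---|---|
| 1 | Electronic consent signed | 5.1, 7.1.3 | Closed |
| 2 | T-MoCA and other screening procedures, within 30 days before baseline | 7.1.3, Appendix 1 | Closed |
| 3 | Eligibility confirmed; a T-MoCA score below 18 excludes | 6.2, 7.1.3 | Closed |
| 4 | Baseline: medical history, Knowledge Assessment Survey, then the in-program questionnaires | 7.1.4 | Opens |
| 5 | Online program and discussion groups | 7.2, 7.3 | Open |

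**1. Can the T-MoCA ever fall inside the window?** Not on the stated order. Section 7.1.4 lets baseline share a day with screening, but only after the screening assessments and confirmation of eligibility. The interval from test to opening of the window therefore runs from the same day up to 30 days. In the same-day case, 11.2 asks for dates of onset and mentions no times, so a date alone could not show on which side of the opening an event fell.

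**2. Would a reaction otherwise qualify as an AE?** Yes. Section 11.0 covers unfavourable symptoms that are non-serious and related in time or cause to study procedures, and 11.2 has a mild grade for events that are easily tolerated. Fatigue after the test fits. Only the start date excludes it.

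**3. What happens to the event for an enrolled participant?** It goes to medical history. The form in Appendix 4 asks about specific conditions (diabetes, hypertension, stroke, seizures, cancer, a diagnosed mental health disorder and similar), surgery and family history. As reproduced, it has no general field for a symptom after a study test and no item on relationship to study procedures. The AE form described in 11.2 does record severity and relatedness, but it is not triggered.

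**4. What happens for a consented person who screens out?** Medical history is a baseline procedure for enrolled participants, so this person does not reach it, and the AE window never opens. No section assigns another record. This is inferred from silence; the protocol does not say that no record is kept.

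**5. Which other named risks are affected?** The online program, the Lifestyle Risk Assessment and the discussion groups all come at or after baseline. Harms from these are inside the window.

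**6. Does the window close consistently?** No. Section 11.0 ends it 30 days after participation ends; 11.1 ends it with the pilot study.

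**The case against.** The strongest reply is that this is a defensible choice with little consequence. Sections 11.0 and 11.1 agree on the start point. The T-MoCA is a 5-10-minute eligibility test and not the product being piloted. No aim or outcome concerns its tolerability, and section 12.1 plans no AE analysis. Participants may skip questions or take breaks, and the 48-hour contact step is not restricted to the period after baseline, so distress at screening need not go unanswered. Most of this stands and limits the size of the point. It does not remove it: the contact step offers support but creates no AE record, and a baseline start sits badly with a protocol that names a risk from an earlier procedure.

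A reader might also infer more than the documents support:

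- **That reactions to the T-MoCA can never be captured.** The window turns on when the event occurs, not on when the test was given. A reaction with onset after baseline opens can be recorded, and 11.0 allows a pre-existing condition that worsens with a study procedure to count as an AE.
- **That events in screen failures are recorded nowhere.** The AE form and any screening form are not reproduced, the data-flow figures are not shown in the text available, and section 13.2 requires source documents. What can be said is that no section assigns such a record.
- **That people scoring below 18 are the most affected.** The documents give no information on who finds the test frustrating, and no event rate.
- **That cognitive testing is the main risk.** It is one of several in 5.2.1.

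**Conclusion.** The point holds in a limited form. Reactions to the T-MoCA with onset before baseline are classified as medical history and not as procedure-related AEs, and section 5.2.1 contradicts section 7.1.3 and Appendix 1 on when the test is given. All 20 planned participants, and every consented person who takes the test and screens out, are exposed to it before the window opens. That counts people exposed, not events lost; the number of events cannot be estimated from the documents.

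The impact is minor. The protocol describes its risks as minimal, the program under evaluation is covered by the window, and no engagement, effectiveness, acceptability or usability result changes. The conclusion assumes that the AE sections are followed as written. The part about screen failures also assumes that no form outside the published text fills the gap.

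**What to change.** - In 11.0 and 11.1, start recording of study-procedure-related AEs at electronic signature of the ICF.
- In both sections, limit the medical-history sentence to events before ICF signature.
- State that the AE form also applies to consented participants who fail screening.
- In 5.2.1, correct the timing of cognitive screening to agree with 7.1.3 and Appendix 1.
- While these sentences are open, choose one end point for the window, since 11.0 and 11.1 give different ones.

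The cost is a wording change in three sections and an AE form that opens one visit earlier. The downside is a few more mild AE entries, including some for people who are never enrolled.
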